6.4 Procedures

Procedures	
Subjects indicated for screening, diagnostic (for minor complaints such as rectal bleeding or minor abdominal pain) or polyp surveillance colonoscopy will meet with the physician or clinical coordinator prior to the procedure for a standard pre-procedure evaluation. Following a preliminary evaluation of eligibility, the patient will be informed of the clinical study and offered the opportunity to participate if he/she is an acceptable candidate. Should the subject agree to join the study, they will be provided a copy of the patient informed consent form and provided ample time to review the form. The point of enrollment will be upon signing the patient informed consent form. Subjects who sign the consent form but do not undergo any procedure will be recorded as screen

-------------------	---

Clinical Investigational Plan			
Protocol ID	934CLD	Sponsor	GI View Ltd.
Revision	03	Investigational Device	Aer-O-Scope® Colonoscope System

	
failures on a separate log, and removed from the enrollment roster.
 
The duration of this multi-national study is expected to be twelve (12) months, three (3) months per site. Each enrolled subject will participate for up to seven (7) days which will include the day of the informed consent signature, the bowel preparation and the day of procedures (Aer-O-Scope Colonoscopy and colonoscopy) with a 24-48 hour follow-up period.
 
Up to 200 subjects will be enrolled in the USA and up to 110 subjects will be enrolled in Israel with a total of up to 310 Subjects overall.

--	--

6.5 Monitoring plan

General Outline Details	A full monitoring plan 935CLD Clinical Investigation Monitoring Plan will be provided separately.
--------------------------------	--

7 STATISTICAL CONSIDERATIONS

Measurements	The pass criteria for the study objectives are rejecting the Null hypotheses as presented below.
Primary Hypothesis:	Colonoscopy with the Aer-O-Scope Colonoscope System will have lower AMR than the conventional forward-viewing colonoscopes.
Statistical Analysis Assumptions:	
 The Adenomas rate within the sample will be 50% (see Appendix 4: Bibliography). The adenoma rate in the sample, for patients with Adenomas, will be 200% (average of 2 adenomas per person). (see Appendix 4: Bibliography) The differences in AMR between the two groups will be 15% (see Appendix 4: Bibliography) The expected AMR of the two groups will be 0.10 vs 0.25 (see Appendix 4: Bibliography) The drop-out rate will be 10%.
Statistical Analysis Plan: Hypotheses testing based calculations	
 For testing the hypothesis that the Aer-O-Scope Colonoscope System will have lower AMR and PMR than the conventional forward-viewing colonoscopies we will perform the Z-tests for comparing two proportions. The tests will be two-sided with significant level of 5%. To demonstrate the physicians proficiency in operation of (including therapeutic interventions) and visualization with the Aer-O-Scope Colonoscope descriptive statistics will be performed using the Likert Scale questionnaire. A mean score between one (1) and three (3) will denote proficiency.
Sample Size Calculation:	The sample size calculation based on the independence AMR between the two groups. A total of 240 patients are needed to compare the AMR between the groups using Z-test for two proportions comparisons. This number enables a 10% dropout, and does not include 70 patients (20-30 training subjects per site (sub-investigator dependent) for learning qualification. This sample size based on a significant level of 5% and a power of 80% to prove a difference in AMR between the groups.

Clinical Investigational Plan			
Protocol ID	934CLD	Sponsor	GI View Ltd.
Revision	03	Investigational Device	Aer-O-Scope® Colonoscope System

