Number of Subjects	
Three hundred and 10 (310):
 
Up to ten (10) training cases per investigator per site) plus eighty (80) study subjects per site (between one hundred (100) and one hundred and ten (110)subjects per site (dependent on the number of investigators including training cases)
 
Each site will have three (3) study cohorts:
 
 ✓ Training cohort (up to the first 10 cases per investigator) Aer-O-Scope colonoscopy followed by conventional colonoscopy (not part of the statistical evaluation for visualization) ✓ Aer-O-Scope colonoscopy followed by conventional colonoscopy ✓ Conventional colonoscopy followed by Aer-O-Scope colonoscopy
Study Duration	One (1) Year

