Study Objectives	
1. Primary Objectives:
 
1.1. To measure the adenoma miss rate (AMR) (based on histology) for the Aer-O-Scope colonoscopy as compared to the AMR for conventional colonoscopy in a tandem back-to-back study.
 
The AMR is defined as the percentage of adenomas missed per cohort (either by the Aer-O-Scope colonoscope or a conventional colonoscope) and is measured by the number of missed adenomas (detected in the second pass colonoscopy) divided by the total number of adenomas detected per cohort.
 
See Number of Subjects above for cohort group definitions
 
1.2. To demonstrate the Aer-O-Scope Colonoscope System is safe for the performance of screening, diagnostic (minor cases such as rectal bleeding and/or abdominal pain) and polyp surveillance colonoscopy.
 
2. Secondary Objectives:
 
2.1. To measure the polyp miss rate (PMR) for the Aer-O-Scope colonoscopy as compared to the PMR for conventional colonoscopy in a tandem back-to-back study.
 
The PMR is defined as the percentage of polyps missed per cohort (either by the Aer-O-Scope colonoscope or a conventional colonoscope) and is measured by the number of missed polyps (detected in second pass colonoscopy) divided by the total number of polyps detected per cohort.
 
(See Number of Subjects above for cohort group definitions).
 
2.2. To measure the advanced adenoma (≥10mm with villous histology or with high grade dysplasia based on histology) miss rate (AAMR) for the Aer-O-Scope colonoscopy as compared to the AAMR for conventional colonoscopy in a tandem back-to-back study.
 
The AAMR is defined as the percentage of advanced adenomas missed per cohort (either by the Aer-O-Scope colonoscope or a conventional colonoscope) and is measured by the number of missed advanced adenomas (detected in second pass colonoscopy) divided by the total number of polyps detected per cohort.

Clinical Investigational Plan

Protocol ID	934CLD	Sponsor	GI View Ltd.
Revision	03	Investigational Device	Aer-O-Scope® Colonoscope System

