6 DESIGN OF THE CLINICAL INVESTIGATION

6.1 General

This will be a prospective multi-center, multi-national comparative non-blinded clinical investigation. Each subject will undergo back-to-back tandem colonoscopies with the Aer-O-Scope Colonoscope System and a conventional colonoscope (for a list of scopes to be used, see Appendix 2) since this is a tandem colonoscopy study, each subject will serve as their own control. The 1st procedure will be randomized, half to Aer-O-Scope Colonoscope System and half to conventional colonoscope. The same investigator will perform both procedures on each subject. All pathologies found will be either removed or tattooed. Unmarked pathologies found on second pass will represent those missed during the 1st pass, thus making the subject and the control one and the same. Tattooed pathologies that can be removed endoscopically will be removed in an additional colonoscopy. This may occur if a large polyp cannot be removed for any reason with the Aer-O-Scope, but can be removed with conventional colonoscopy.

Subjects will be randomized in blocks of twenty (20) for either Aer-O-Scope or conventional colonoscopy as the first procedure. Physicians will be notified of the procedural order immediately prior to first colonoscopy. Up to the first ten (10) cases for each physician (system operation training cases) will all begin with the Aer-O-Scope colonoscopy as the first procedure.

The primary endpoint of AMR was chosen as this measure appears to be related to the performance of colonoscopy and reduction in colorectal cancer incidence. During the course of the last decade, several major visualizations studies have been performed and it has become common practice to use the “second-pass” method for measuring colonoscopy visualization methods^{iii,iv}. In the “second-pass” method, during the course of the first colonoscopy, all visualized lesions are removed (or tattooed in the event that they cannot be removed for any reason.). Any unmarked abnormalities discovered during the second pass colonoscopy are considered to be missed pathologies for the first pass colonoscopy.

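### The two-proportion Z-test for AMR and PMR ignores within-patient correlation, so the 5% two-sided level holds only if lesions in one patient are independent

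*Combined protocol and SAP*

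**What the plan says.** Section 6.1 randomises patients to procedure order: "Subjects will be randomized in blocks of twenty (20) for either Aer-O-Scope or conventional colonoscopy as the first procedure". The synopsis (Section 1.5) defines AMR on lesions pooled over patients: it "is measured by the number of missed adenomas (detected in the second pass colonoscopy) divided by the total number of adenomas detected per cohort". Section 7 then states that "we will perform the Z-tests for comparing two proportions. The tests will be two-sided with significant level of 5" per cent, for both AMR and PMR, and makes rejection of the null hypothesis the pass criterion.

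Among its assumptions, Section 7 lists: "The adenoma rate in the sample, for patients with Adenomas, will be 200% (average of 2 adenomas per person". The only independence it mentions is between groups: "The sample size calculation based on the independence AMR between the two groups". It closes with: "This sample size based on a significant level of 5% and a power of 80% to prove a difference in AMR between the groups". Nowhere do the documents mention an ICC, a design effect, a robust variance, a mixed or GEE model, or a patient-level test.

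**The concern.** The unit of randomisation is the patient; the unit of the test is the adenoma. All adenomas from one patient fall in one cohort, and they share one bowel preparation, one anatomy and one first pass by one endoscopist. Positive correlation of misses is therefore plausible. Replacing subjects with a Boston score of 0 or 1 (Section 6.1) narrows the variation in preparation, but scores 2 and 3 remain, as do anatomy and the quality of the pass.

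At any positive ICC, with more than one adenoma in some patients, the binomial variance behind the Z-test is too small, and more so when adenoma counts vary between patients. Because rejecting the null is the pass criterion, the risk falls directly on the superiority claim: a false finding that Aer-O-Scope misses fewer adenomas would occur more often than its nominal 2.5%. A test that corrects the variance has less power than the independence calculation suggests.

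**Working it through.** **Inputs from the plan.** Section 7: AMR 0.10 versus 0.25, two-sided 5%, power 80%, half of patients with an adenoma, mean 2 adenomas in those patients, dropout 10%, 240 patients. Section 1.5: "eighty (80) study subjects per site"; three sites. Section 6.1: blocks of 20, half to each order.

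**Inputs assumed, because the documents do not give them.** ICC 0.1, 0.2 and 0.3. Adenoma count m per affected patient with mean 2: always 2, 1 + Poisson(1), or geometric. Blocks nested within site.

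**Step 1: the plan's own sample size.** Pooled two-proportion formula, with mean proportion 0.175:

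n = [1.96 × √(2 × 0.175 × 0.825) + 0.8416 × √(0.10 × 0.90 + 0.25 × 0.75)]² / 0.15² = 99.54 adenomas per arm.

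At 0.5 × 2 = 1 adenoma per patient and 10% dropout, that is 2 × 99.54 / 0.9 = 221.2, about 222 patients. The plan states 240, which equals 3 × 80, and does not show its conversion. Working forward: 240 × 0.9 × 0.5 × 2 = 216 adenomas, or 108 per arm. Power under full independence is Φ[(0.15 × √108 − 1.0532) / 0.5268] = Φ(0.960) = 0.831. So 240 carries a small surplus: 108 / 99.54 = 1.085.

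**Step 2: design effect.** DE = 1 + (E[m²]/E[m] − 1) × ICC. For the three count distributions E[m²]/E[m] is 4/2 = 2, 5/2 = 2.5 and 6/2 = 3, so DE is 1 + ICC, 1 + 1.5 × ICC and 1 + 2 × ICC.

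**Step 3: by formula.** The planned test's two-sided error is 2 × [1 − Φ(1.96/√DE)]. Power of a valid test comes from 108/DE effective adenomas per arm.

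| DE | Example | Z-test error | Valid-test power |
|---|---|---|---|
| 1.1 | ICC 0.1, equal counts | 6.2% | 79% |
| 1.2 | ICC 0.1, geometric | 7.4% | 76% |
| 1.3 | ICC 0.3, equal counts | 8.6% | 72% |
| 1.6 | ICC 0.3, geometric | 12.1% | 63% |

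**Step 4: by simulation.** 216 evaluable patients in 12 blocks (3 sites × 4 blocks, 9 evaluable per order in each block); beta-binomial misses; null AMR 0.175. There were 40,000 replicates for the Z-test, and 20,000 with 999 permutations for a studentised permutation test that re-assigns whole patients within blocks. Ranges span the three count distributions.

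| ICC (assumed) | Z-test, two-sided error | False claim that Aer-O-Scope is lower (nominal 2.5%) | Power, permutation test |
|---|---|---|---|
| 0 | 5.0-5.2% | 2.5-2.6% | 82-83% |
| 0.1 | 6.3-7.4% | 3.2-3.7% | 76-80% |
| 0.2 | 7.5-9.7% | 3.8-4.8% | 70-76% |
| 0.3 | 8.6-12.1% | 4.4-5.9% | 65-73% |

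Under the null the permutation test rejects in 4.9-5.3%. A linearised robust-variance test is slightly liberal (5.4-5.9%), so its somewhat higher power is not used here.

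**Step 5: how much correlation 240 can absorb.** Power stays at 80% while DE ≤ 1.085, that is, up to an ICC of 0.085 (equal counts) or 0.085/2, about 0.04 (geometric). Patients for 80% power are 221.2 × DE: at ICC 0.1-0.3, 244-288 (equal counts) or 266-354 (geometric).

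**PMR.** The mechanism is the same, but the plan assumes no polyp rate or PMR, so the size cannot be computed.

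**The case against.** The strongest reply is that everything beyond the direction of the effect rests on an ICC the documents do not give. At ICC 0 the planned test is correct, and at 0.1 its error is only 6.3-7.4%. The larger figures need both a higher ICC and uneven counts. That is fair and is why every figure is conditional. But the 5% level then depends on an assumption the plan neither states nor supports.

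A second reply is that Section 6.1 replaces subjects who cannot undergo tandem colonoscopy. If replacement were complete there would be 240 evaluable patients and 120 adenomas per arm. By formula, power would be 86.9% at ICC 0, 80-84% at 0.1 and 68-77% at 0.3, and the tolerated design effect would be 120/99.54 = 1.206 (ICC about 0.10 to 0.21). This reading stands as the favourable case. Section 7, however, says that 240 already allows for 10% dropout, which gives 216. Replacement does nothing for type I error.

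Third, some correlation may come from site or endoscopist, which blocking within site would largely balance. In a simulation with site differences only (AMR 5%, 17.5% and 30%; ICC 0.07; geometric counts) the Z-test error was 5.7%, against about 6.7% from the design-effect formula. So inflation is smaller if correlation is of that kind, but it remains.

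Fourth, Section 6.1 says each subject is their own control. That does not remove the problem: a patient contributes misses only to the cohort of the first-pass device, so the comparison is between patients.

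Finally, the permutation result assumes equal evaluable numbers per order. Sections 6.1 to 6.3 withdraw patients with large polyps after a conventional first pass but not after an Aer-O-Scope first pass, so exchangeability among evaluable patients is not assured. That limitation is real and applies equally to the Z-test.

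**Conclusion.** The concern holds. As written, the primary test uses the wrong variance whenever misses are positively correlated within a patient, and its two-sided error then exceeds 5%. The direction is certain for any positive ICC with multiple adenomas in some patients. The size is not known from the documents: about 6-7% at an assumed ICC of 0.1 and about 9-12% at 0.3. The stated 80% power is met under independence (83% with 216 evaluable patients) but is lost beyond an ICC of about 0.04 to 0.085, or about 0.10 to 0.21 if all 240 patients are evaluable. Adenoma-level independence is inferred from the pooled AMR definition and the plain Z-test; the plan does not state it. Because this test decides whether the trial passes, and a change made after the results are seen would not be credible, it must be fixed beforehand.

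**What to change.** In Section 7, keep the AMR definition and the two-sided 5% level, and replace the Z-test for AMR and PMR as follows.

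- **Estimate:** compare the cohort miss rates as ratio estimators with a patient-level robust variance. A binomial GEE with patient as cluster, adjusted for site, is an acceptable alternative; name one as primary.
- **Decision:** take the p-value from a permutation test that re-assigns whole patients to procedure order within site and randomisation block. State whether blocks are nested within site, which Section 6.1 leaves open.
- **Analysis set:** confirm that the non-randomised training cases stay out, as Sections 1.5 and 2 already provide.
- **Power:** state about 83% with 216 evaluable patients if adenomas within a patient are independent, and lower if the ICC is positive. Give any range only with its ICC, adenoma-count and evaluable-patient assumptions.

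Keeping 240 patients is acceptable if this is disclosed; restoring 80% power at a positive ICC would take the larger numbers in Step 5.

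The cost is SAP wording, a few lines of code, and the block identifier kept in the analysis dataset. No new patients or data are needed. The price is a less favourable, conditional power statement.

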5 HYPOTHESES OF THE CLINICAL INVESTIGATION

Hypotheses	
1. Primary Hypotheses:
 
1.1. Colonoscopy with the Aer-O-Scope Colonoscope System will have lower AMR than the conventional forward-viewing colonoscopes. The mean adenoma miss rate for conventional colonoscopy as found in the published literature is between 15-40%.
 
The number missed adenomas (NMA) (based on histology) for each of the two cohort groups in back-to-back tandem colonoscopy will be measured.
 
The NMA is defined as the number of adenomas (based on histology) detected during the second pass colonoscopy that were not detected and removed (or tattooed) during the first pass colonoscopy.
 
The AMR will be measured by the NMA divided by the total number of adenomas detected (for each cohort).
 
1.2. Colonoscopy with the Aer-O-Scope Colonoscope System is safe for screening, diagnostic and surveillance colonoscopy.
 
2. Secondary Hypotheses:
 
2.1. Colonoscopy with the Aer-O-Scope Colonoscope System will have a lower PMR than the conventional forward-viewing colonoscopes.
 
The number missed polyps (NMP) for each of the two cohort groups in back-to-back tandem colonoscopy will be measured.
 
The NMP is defined as the number of polyps detected during the second pass colonoscopy that were not detected and removed (or tattooed) during the first pass colonoscopy.
 
The PMR will be measured by the NMP divided by the total number of adenomas detected (for each cohort).
 
2.2. Colonoscopy with the Aer-O-Scope Colonoscope System will have lower AAMR than the conventional forward-viewing colonoscopes.
 
The number missed advanced adenomas (NMAA) (based on histology) for each of the two cohort groups in back-to-back tandem colonoscopy will be measured.
 
The NMAA is defined as the number of advanced adenomas (based on histology) detected during the second pass colonoscopy that were not detected and removed (or tattooed) during the first pass colonoscopy.
 
The AAMR will be measured by the NMAA divided by the total number of adenomas detected (for each cohort). Because approximately only 6% of all adenomas are considered advanced adenomas, the evaluation of this objective will most likely not

-------------------	--

Clinical Investigational Plan			
Protocol ID	934CLD	Sponsor	GI View Ltd.
Revision	03	Investigational Device	Aer-O-Scope® Colonoscope System

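### The primary AMR and PMR test pools adenomas across three sites and treats those from one patient as independent; a site-stratified, patient-clustered analysis is a cheap improvement

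*Combined protocol and SAP*

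**What the plan says.** - **Test.** Section 7 states, for AMR and PMR, that "we will perform the Z-tests for comparing two proportions", two-sided at 5%. No stratified, adjusted, clustered or sensitivity analysis appears in the plan.
- **Unit.** Sections 1.5 and 5 define AMR as missed adenomas over all adenomas detected in the cohort, so the unit is the adenoma. Section 7 expects half the subjects to have adenomas, with two each on average in those who do.
- **Sites.** Section 1.5: "Each site will have three (3) study cohorts". One is the training cohort, which is left out of the visualization analysis; the other two are the two procedure orders. There are three sites with 80 study subjects each.
- **Allocation.** Section 6.1: "Subjects will be randomized in blocks of twenty (20"). No stratification factor is named. The same investigator performs both passes in a given subject.
- **Site differences.** Section 6.2 lets each site use its usual colonoscopes and its clinic's standard preparation. Section 6.4 places the sites in two countries.
- **Miss rates.** Section 5: "The mean adenoma miss rate for conventional colonoscopy as found in the published literature is between 15-40"%. Section 7: "The expected AMR of the two groups will be 0.10 vs 0.25".

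**The concern.** The pooled Z-test leaves out two features of the data.

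First, site. Blocking balances subjects, not adenomas, and adenomas are what the test counts. If sites differ in miss rate, chance differences in where each cohort's adenomas come from add noise that a within-site comparison would remove.

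Second, patient. Two adenomas in one patient share the same bowel preparation, anatomy and operator, so their chances of being missed are likely to be correlated. The independence mentioned in Section 7 is between the two groups; it does not cover lesions within a patient. If they are correlated, the binomial variance is too small and the nominal 5% test rejects too often. What is at stake is a modest amount of precision from the first feature and the error rate of the primary claim from the second.

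**Working it through.** **1. The plan's own figure.** Inputs from Section 7: 0.25 vs 0.10, two-sided 5%, 80% power, 0.5 × 2 = 1.0 adenoma per subject, 10% dropout.

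n per group = [1.960·√(2 × 0.175 × 0.825) + 0.842·√(0.25 × 0.75 + 0.10 × 0.90)]² / 0.15² = (1.053 + 0.443)² / 0.0225 ≈ 99.5, so 100 adenomas per group. That is 200 subjects, and 200/0.9 gives 223. With continuity correction it is 113 per group, 226 subjects, and 226/0.9 gives 252. The stated 240 lies between these and equals 3 × 80. With 240 × 0.9 = 216 completers there are 108 adenomas per group, and power = Φ[(0.15·√108 − 1.053)/0.527] = Φ(0.96) = 83.1%. On its own assumptions the plain test is adequately sized.

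**2. Variance removed by site.** The documents give no between-site spread. Assume conventional AMR of 15%, 25% and 40% at the three sites (the literature range in Section 5) and Aer-O-Scope at 0.4 times these.
- Conventional: mean within-site p(1−p) = (0.1275 + 0.1875 + 0.2400)/3 = 0.1850. Pooled: 0.2667 × 0.7333 = 0.1956. Ratio 0.946.
- Aer-O-Scope (6%, 10%, 16%): 0.0936 against 0.0953. Ratio 0.982.
- Both arms: (0.1850 + 0.0936)/(0.1956 + 0.0953) = 0.958, a reduction of about 4%.

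**3. Power, pooled Z against a site-stratified Mantel-Haenszel test.** Simulated, adenomas independent, about 36 per site and cohort:

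| Assumed conventional AMR by site | Aer-O-Scope | Pooled Z | Stratified |
|---|---|---|---|
| 25% at all | 10% | 83.7% | 83.3% |
| 20/25/30% | × 0.4 | 83.7% | 83.6% |
| 15/25/40% | × 0.4 | 86.4% | 87.1% |
| 15/25/40% | × 0.5 | 69.5% | 70.6% |
| 7/21/47% | 2/7/21% | 83.2% | 87.1% |

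A second simulation with no spread gave 83.9% vs 83.2%, so the loss there is roughly half a point. Type I error of the pooled test was 5.0-5.1% at the 15-40% spread. It reached 5.8% (stratified 5.0%) only at the extreme spread in the last row.

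**4. Endoscopist strata.** Their number is not given in the text supplied. Seventy training patients at up to ten per investigator suggest about seven. With seven strata, power fell from 84.0% to 82.8% with no spread, and from 88.0% to 87.6% with AMRs spread evenly over 15-40%.

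**5. Clustering within patient.** Design effect = 1 + (m* − 1)·ICC, where m* = E(m²)/E(m) for the number of adenomas m in a patient who has any. A mean of 2 gives m* = 2.5 if m is 1 + Poisson(1), and m* = 3 if m is geometric. The actual type I error of a nominal 5% test is 2[1 − Φ(1.96/√DE)]:
- ICC 0.1: DE 1.15 to 1.20, error 6.8% to 7.4%.
- ICC 0.2: DE 1.30 to 1.40, error 8.6% to 9.8%.

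Simulation agrees: 6.5-8.9% in one set and 7.5-9.4% in another. Stratifying by site without clustering leaves it at 6.4-8.6%. A site-stratified test with patient-clustered variance gives about 5.6-5.9%. With 108 adenomas per group, power falls from 83.1% to 77.6-75.9% at ICC 0.1 and to 72.4-69.2% at ICC 0.2. The ICC values are assumptions; the documents give none.

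**The case against.** The strongest reply is that site adjustment is not shown to help. The 15-40% in Section 5 is a range of published means, not a spread across three sites in one trial. Expert operators (Section 2), exclusion of training cases and replacement of poorly prepared subjects (Section 6.1) may narrow the differences. With milder or no spread the stratified test gains nothing or loses slightly, and the pooled test holds its level at the 15-40% spread. A GEE logistic model would also replace a difference in proportions by an odds ratio.

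All of this stands against four stronger readings that a reader might infer:

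- **That site adjustment is free precision.** Its sign depends on a spread that the documents do not give.
- **That the trial is known to be randomised in blocks within site and that every investigator performs both orders.** The first is a fair inference (80 = four blocks of 20) but is not stated. On the second, Section 6.1 says only that one investigator does both passes in a subject.
- **That miss rates are known to depend on the operator, so endoscopist belongs in the primary model.** The plan expects a learning curve but never says this, and sparse strata can cost power.
- **That 240 is too small.** It is not under the plan's own assumptions, and the documents give no ICC from which to show otherwise.

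The reply does not reach the clustering argument. Step 5 does not depend on sites differing, and a Mantel-Haenszel-weighted risk difference keeps the difference in proportions.

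**Conclusion.** The point holds as a cheap improvement. The primary AMR and PMR analysis ignores site in a trial that runs both orders at every site, and it treats lesions from one patient as independent. The site part is small: about 4% of variance and 0.7 to 1 point of power at an assumed 15-40% spread, nothing at 20-30%, and about 0.5 points lost with none. The patient part is larger and concerns validity: at an assumed ICC of 0.1-0.2, type I error is about 7.5-9.4% with the pooled test and about 5.6-5.9% with the clustered one. If the ICC is near zero, this benefit disappears. The documents do not show that the pooled test is invalid because of site, or that the trial is under-sized.

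**What to change.** 1. State in Section 6.1 whether the blocks of 20 are stratified by site.
2. In Section 7, prespecify for AMR and PMR a site-stratified primary analysis with patient as the cluster. A Mantel-Haenszel-weighted risk difference with patient-clustered variance keeps the planned effect measure; GEE with site is an alternative, with its effect measure named.
3. Name a small-sample correction for the robust variance. Only about 36 × 0.5 = 18 adenoma-positive patients are expected per site and cohort, and the clustered test still sits slightly above 5%.
4. Use endoscopist only in a sensitivity analysis, and report AMR by site and cohort.

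Cost: a short paragraph of SAP text and slightly more complex programming, settled before results are seen. No new data are needed, because each polyp already goes to histology as a single specimen (Section 6.2). The price is a small loss of power if sites are alike, and a lower, more realistic power if adenomas cluster.
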